5.3.5.2 Non-hematologic Toxicity

Gastrointestinal Toxicity, Nausea and Vomiting

All patients should receive antiemetics* to prevent nausea and vomiting. Steroids and 5-HT3 antagonists are required premedications but additional specific antiemetic therapy is left to the discretion of the treatment physician. If vomiting is severe, consider hospital admission and/or use of aprepitant if possible. Do not modify chemotherapy doses.

*Aprepitant, when given once daily for 14 days as a 100 mg capsule with an oral contraceptive containing 35 mcg of ethinyl estradiol and 1 mg of norethindrone, decreased the AUC of ethinyl estradiol by 43% and decreased the AUC of norethindrone by 8%. Women of childbearing potential using pregnancy contraception that includes ethinyl estradiol should not receive Aprepitant for the treatment of nausea/delayed emesis. Patients may change to a different method of contraception if they wish to use Aprepitant.

Hepatotoxicity

Bilirubin	Etoposide*
≤ 1.5 X ULN	100%
> 1.5 – 3.0 X ULN	50%
> 3.0 X - ≤ 5.0 ULN	30%
> 5 X ULN	Hold**

* Please note that the % dose administered is based on the original starting dose of etoposide (100 mg/m²). If patient is at dose level -1 or -2, % should be based on reduced dose the patient is currently on, not original dose.

** For bilirubin greater than 5 X ULN it is recommended not to use etoposide for that cycle but this is at the discretion of the treating physician. If holding, repeat labs on a weekly basis for

up to 3 weeks until total bilirubin is \leq 5 X ULN. The cisplatin dose should also be held if etoposide is held so that all drugs are kept on the same schedule. If bilirubin improves within 3 weeks to \leq 5 X ULN, then resume treatment and use reduced dose per table above. If bilirubin does not improve to \leq 5 X ULN within 4 weeks, discontinue protocol therapy.

Hypomagnesemia

Hypomagnesemia is not an indication for stopping therapy. Oral or parenteral magnesium supplementation is indicated for serum magnesium levels $<$ 1.5 mEq/L.

Allergic Reactions

Discontinue all protocol treatment promptly if \geq grade 3 anaphylaxis develops.

Suggested Management of Allergic Reaction:

In case of mild allergic symptoms (e.g., appearance of a localized or generalized pruritus), symptomatic treatment may be given (e.g., oral antihistamine or corticosteroids).

Patient experiencing significant allergic reaction should be managed according to local institutional standards. A combination of corticosteroids, antihistamines, nebulized respiratory therapy with beta (2) agonists and isotonic fluid support should be employed as appropriate based on patient's clinical condition.

For Grade 3 or Grade 4 symptoms: (Grade 3: severe reaction; prolonged [i.e., not rapidly responsive to symptomatic medication and/or brief interruption of infusion]; recurrence of symptoms following initial improvement; hospitalization indicated for other clinical sequelae [e.g., renal impairment, pulmonary infiltrates]; Grade 4: life-threatening; pressor or ventilatory support indicated):

- Immediately discontinue chemotherapy infusion. Begin an i.v. infusion of normal saline and treat the subject as follows: Recommend bronchodilators, epinephrine 0.2 to 1 mg of a 1:1,000 solution for subcutaneous administration, 0.3 mg of a 1:1,000 solution for intramuscular administration, or 0.1 to 0.25 mg of a 1:10,000 solution slowly for i.v. administration, and/or diphenhydramine 50 mg i.v. with methylprednisolone 100 mg i.v. (or equivalent), as needed. Subject should be monitored until the Investigator is comfortable that the symptoms will not recur. Cisplatin will be permanently discontinued. Investigators should follow their institutional guidelines for the treatment of anaphylaxis. Remain at bedside and monitor subject until recovery from symptoms.

Grade 3 or 4 Non-Hematologic Toxicity

If patient develops grade 3 or 4 non-hematologic toxicity attributed to protocol therapy but not detailed above, hold all therapy. These can be restarted if the toxicity has resolved to < grade 1 by the time of the next treatment. Doses of Etoposide should then be reduced according to the Etoposide Dose Level Table (taking into consideration the treatment dose used in the prior cycle).

5.4 Supportive Care

- 5.4.1 All supportive measures consistent with optimal patient care will be given throughout the study.
- 5.4.2 Ondansetron or an equivalent 5HT3 antagonist is required as a premedication 30-60 minutes prior to temozolomide (Arm A).
- 5.4.3 Ondansetron or an equivalent 5HT3 antagonist and dexamethasone are required premedications prior to administration of platinum and etoposide (Arm B).
- 5.4.4 Hydration and/or diuresis for patients in Arm B is permitted and may be conducted per institutional guidelines.
- 5.4.5 In the event of platinum extravasation, apply a warm pack to reduce local discomfort and notify the treating physician of the extravasation. If indicated, restart peripheral IV in a larger vein.
- 5.4.6 For management of allergic reactions to cisplatin, see Suggested Management of Allergic Reactions under Section [5.3.5.2](#).
- 5.4.7 Patients must maintain adequate hydration and urinary output. Patients, on both arms, should be advised to increase oral fluid intake during treatment.
- 5.4.8 Aprepitant may be considered as an additional antiemetic for patients experiencing severe nausea and vomiting in Arm B. Caution with use of this medication should be considered as outlined in Section [5.1.2](#) in regard to female patients using oral contraceptive agents. All other antiemetic administration may be left to the discretion of the treating physician.
- 5.4.9 Appropriate supportive measures including Imodium and/or Lomotil should be implemented immediately to prevent dehydration should diarrhea develop.
- 5.4.10 The use of growth factors (filgrastim, sargramostim or pegfilgrastim) is permitted in both arms of the study and should be administered in accordance with ASCO guidelines (54).
- 5.4.11 The use of erythropoietin stimulating agents is NOT permitted. Anemia may be managed with blood transfusions as indicated.
- 5.4.12 Concomitant aminoglycoside antibiotic use should be avoided during platinum therapy until patient has fully recovered (i.e., at least 4 weeks from last dose of platinum).

- 5.4.13 Use of bisphosphonates or denosumab is allowed for patients with bone metastasis or hypercalcemia.
- 5.4.14 Anxiolytics and analgesics may be provided at physicians' discretion.
- 5.4.15 Supplemental pyridoxine (vitamin B6) is contraindicated in patients receiving cisplatin and may not be administered in patients on Arm B.

5.5 Duration of Therapy

Patients will receive protocol therapy unless:

- 5.5.1 Extraordinary Medical Circumstances: If at any time the constraints of this protocol are detrimental to the patient's health, protocol treatment should be discontinued. In this event submit forms according to the instructions in the EA2142 Forms Packet.
- 5.5.2 Patient develops disease progression per Section [6.1.4](#).
- 5.5.3 Patient withdraws consent.
- 5.5.4 Patient experiences unacceptable toxicity
- 5.5.5 Non-protocol medical cancer therapies are administered. Localized surgical interventions or radiation intervention for a second primary malignancy may be permitted but should be discussed with the study chair prior to initiation.

5.6 Duration of Follow-up

For this protocol, all patients, including those who discontinue protocol therapy early, will be followed for response until progression, even if non-protocol therapy is initiated, and for survival for 5 years from the date of randomization. All patients must also be followed through completion of all protocol therapy.

6. Measurement of Effect

6.1 Antitumor Effect – Solid Tumors

For the purposes of this study, patients should be re-evaluated for response every 8 weeks. In addition to a baseline scan, confirmatory scans should also be obtained 4 weeks following initial documentation of objective response.

Response and progression will be evaluated in this study using the international criteria proposed by the revised Response Evaluation Criteria in Solid Tumors (RECIST) guideline (version 1.1) [Eur J Ca 45:228-247, 2009]. Changes in the largest diameter (unidimensional measurement) of the tumor lesions and the shortest diameter in the case of malignant lymph nodes are used in RECIST.

The following general principles must be followed:

1. To assess objective response, it is necessary to estimate the overall tumor burden at baseline to which subsequent measurements will be compared. All baseline evaluations should be performed as closely as possible to the beginning of treatment and never more than four weeks before randomization.
2. Measurable disease is defined by the presence of at least one measurable lesion.
3. All measurements should be recorded in metric notation by use of a ruler or calipers.
4. The same method of assessment and the same technique must be used to characterize each identified lesion at baseline and during follow-up.

6.1.1 Definitions

Evaluable for Objective Response

Only those patients who have measurable disease present at baseline, have received at least one cycle of therapy, and have had their disease re-evaluated will be considered evaluable for response. These patients will have their response classified according to the definitions stated below.

NOTE: Patients who exhibit objective disease progression prior to the end of cycle 1 will also be considered evaluable.

Evaluable Non-Target Disease Response

Patients who have lesions present at baseline that are evaluable but do not meet the definitions of measurable disease, have received at least one cycle of therapy, and have had their disease re-evaluated will be considered evaluable for non-target lesion assessment. The response assessment is based on the presence, absence, or unequivocal progression of the lesions.

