6.1.4.4 Evaluation of Best Overall Response

The best overall response is the best response recorded from the start of the treatment until disease progression/recurrence or non-protocol therapy (taking as reference for progressive disease the smallest measurements recorded since the treatment started). The patient’s best response assignment will depend on the achievement of both measurement and confirmation criteria.

For Patients with Measurable Disease (i.e., Target Disease)

Target Lesions	Non-Target Lesions	New Lesions*	Best Overall Response	Remarks
CR	CR	No	CR	≥ 4 wks. Confirmation
CR	Non-CR/Non-PD***	No	PR	
CR	Not evaluated	No	PR	
PR	Non-PD***/not evaluated	No	PR	
SD	Non-PD***/not evaluated	No	SD	Documented at least once ≥ 8 wks. from study entry
PD	Any	Yes or No	PD	No prior SD, PR or CR
Any	PD**	Yes or No	PD***	
Any	Any	Yes	PD	

* See RECIST 1.1 manuscript for further details on what is evidence of a new lesion.

** In exceptional circumstances, unequivocal progression in non-target lesions may be accepted as disease progression.

***PD in non-target lesions should not normally trump target lesion status. It must be representative of overall disease status change, not a single lesion increase. Please refer to the Evaluation of Non-Target Lesions – Progressive Disease section for further explanation.

NOTE: Patients with a global deterioration of health status requiring discontinuation of treatment without objective evidence of disease progression at that time should be reported as “*symptomatic deterioration*.” Every effort should be made to document the objective progression even after discontinuation of treatment.

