9.2 Revised statistical plan after Spring 2019 DSMC recommendation (July 2019)

Sample size with power justification

Accrual on this study has been lower than expected, averaging 1-2 patients per month. The ECOG-ACRIN DSMC reviewed this study in Spring 2019 and made the recommendation to modify the statistical plan to reduce the required power of the study to 80% in order to achieve a more realistic sample size and timeframe. Therefore, a total of 80 patients will now be the accrual target to achieve 78 randomized eligible cases. The study seeks to establish an improvement in the primary endpoint, which is defined as a 67% improvement in median progression-free survival (PFS) from 6 months in the control arm (Arm B) to 10 months in the experimental arm (Arm A). The study is now designed to have 80% power for this 40% reduction in the hazard rate with 71 PFS events at full information which is now expected to occur after 75 months of accrual and 7 additional months of follow-up. The primary comparison remains a log-rank test at a one-sided significance level of 0.10. Under exponential distributions the hypothesized reduction corresponds to 1-year progression-free survival of 44% in Arm A versus 25% in Arm B.

Analysis plan including plans for formal interim analysis

The primary analysis set will include all randomized eligible patients. Progression-free survival (PFS) is defined as time from randomization to documented progression or death without progression. Patients without documented progression or death reported will be censored at the time of the last documented disease evaluation. In the secondary analyses, overall survival (OS) is defined as time from randomization to death from any cause, censoring cases who are alive at the date of last contact. Kaplan-Meier estimates will be used for event-time distributions. PFS and OS by arm will be compared using one-sided stratified log-rank tests. Stratified Cox's proportional hazards models will be used to estimate hazard ratios. Response rate (complete response or partial response) and toxicity are also secondary endpoints. Response rate will be analyzed using a Fisher's exact test at a one-sided significance level of 0.10.

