Patient demographics and disease characteristics will be compared using two-sample t-tests or Fisher's exact tests as appropriate. We will also conduct exploratory subset analyses with respect to PFS, OS, and response rate to evaluate the prognostic significance of Ki-67 with regard to these clinical endpoints.

Toxicity will be evaluated among all treated patients regardless of eligibility and interim analyses of toxicity are performed twice yearly for all ECOG-ACRIN studies. With 39 eligible patients per arm, the study will have sufficient precision to provide 90% confidence interval on toxicity that will be no wider than 28%. For rare toxicities with 4% true probability, there will be 80% probability of observing

one or more toxicities on either treatment arm. Formal comparison of toxicity rates between the arms is not a goal of this trial and the sample size will provide sufficient power for detecting only relatively large differences in adverse events.

This study will include one interim analysis of PFS for efficacy at approximately 48 months from the start of accrual (possibly near April 2020), which should correspond to 36 failures under the alternative hypothesis or 50% information time). A log rank test using an O'Brien-Fleming boundary will be conducted and under the alternative hypothesis there is probability of 0.29 that the efficacy boundary will be crossed. Regarding futility, if at the interim analysis the estimated hazard ratio for experimental/control is ≥ 1 the study will be reported as negative. If the estimated hazard ratio is less than 1 but the efficacy boundary is not crossed, the study will have its final analysis at 82 months of study. Results of the interim analysis will be presented to the ECOG-ACRIN Data Safety Monitoring Committee (DSMC) when appropriate.

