9.7 Correlative Studies Statistics

9.7.1 Pathology samples will be collected from all eligible patients. Ki-67 will be determined using immunohistochemical analysis and will be reported as a percentage ranging from 0-100%, based on counting at least 500 tumor cells in the regions with the highest labeling rate ("hot spots")

The primary analysis of Ki-67 will be to evaluate the interaction, if any, between Ki-67 as a continuous measure and treatment. Cox regression or logistic regression, as appropriate, will be used to identify whether the treatment effect varies by Ki-67 for PFS, OS, and RR. Subsequent analyses to identify "optimal" cutpoints from continuous Ki-67 measurement are considered exploratory.

Receiver operating characteristics (ROC) analysis will also be performed to determine the optimal cutoff value in Ki-67 that defines patients with prolonged OS, where prolonged OS is defined as survival of at least 12 months. Hence in these analyses, survival will be considered as a binary endpoint. This optimal cutoff will serve for differentiating patients with features that are clinically more consistent with a well differentiated non-small cell gastrointestinal neuroendocrine tumor from the analysis set.

For the series of Ki-67 values observed in the data, Youden's index will be calculated and with the highest index we will identify the threshold that minimizes the false positive and false negative rates for best detecting prolonged OS. Optimal cutoff values of Ki-67 with respect to response to temozolomide and capecitabine will be determined in similar exploratory manner but the analysis will differ in that we will only include patients whose Ki-67 and response to temozolomide and capecitabine are available. Response to temozolomide and capecitabine is defined as complete response or partial response defined by RESIST 1.1 following initiation of therapy.

Concordance between Ki-67 measured centrally versus registering institutions' pathology assessments will also be investigated and reported. Intra-class correlation will be calculated to assess agreement amongst the two continuous measures.

We will also assess the prognostic significance of well differentiated versus poorly differentiated non-small cell gastroenteropancreatic neuroendocrine tumors in relationship to survival and response to treatment in a similar manner, via Cox proportional hazard models for time to event endpoint and logistic regression for objective response.

Rev. 2/17

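### The response-rate test has no stated denominator and no rule for unassessed patients, and the planned Fisher test is conservative and ignores the randomization strata (minor; secondary endpoint)

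*Combined protocol and SAP*

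**What the plan says.** Section 9.2 (analysis plan) opens with one analysis set: "The primary analysis set will include all randomized eligible patients". For the time-to-event endpoints it states "PFS and OS by arm will be compared using one-sided stratified log-rank tests". Response rate, defined as complete or partial response, is a secondary endpoint analysed with Fisher's "exact test at a one-sided significance level of 0.10". No denominator is given there. The one stated departure from the analysis set is for safety: "Toxicity will be evaluated among all treated patients regardless of eligibility".

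Section 6.1.1 limits who is evaluable. Only patients with measurable disease at baseline who "have received at least one cycle of therapy, and have had their disease re-evaluated will be considered evaluable for response" have their response classified, with one extension: "Patients who exhibit objective disease progression prior to the end of cycle 1 will also be considered evaluable". Section 6.1.4.4 sets the window: "The best overall response is the best response recorded from the start of the treatment until disease progression/recurrence or non-protocol therapy". Its table of best overall response has no row for a patient who was never assessed. Section 4.5 keeps collecting data on patients who never start treatment.

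Section 9.7.1 uses a restricted set for one exploratory cutoff analysis, where "we will only include patients whose Ki-67 and response to temozolomide and capecitabine are available". That rule does not cover the Fisher test.

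**The concern.** Sections 9.2 and 6.1.1 describe different groups, and neither refers to the other. A patient who is never treated, who dies before any re-evaluation, or who deteriorates and is never re-imaged belongs to the 9.2 set but receives no classification under 6.1.1. If 6.1.1 became the denominator, inclusion would depend on what happened after randomization. That biases the arm comparison if such losses differ by arm. They could differ, because a cycle is 28 days in Arm A and 21 days in Arm B.

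The second matter is the choice of test. Response is the only formally tested efficacy endpoint that does not use the randomization strata of Section 4.3 (ECOG PS 0-1 vs 2; GI vs pancreatic). Fisher's test also spends well under its nominal 0.10 at this sample size.

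**Working it through.** **Plan's own figures.** No power figure is given for response, so the check starts with the design inputs for PFS in 9.2 (hazard ratio 0.60, one-sided 0.10, 80% power). Schoenfeld's formula gives 4(1.2816+0.8416)²/(ln 0.6)² = 18.03/0.2609 = 69.1, so 70 events. At the planned 71 events, power is 80.8%. The design reproduces.

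**Inputs for response.** 39 eligible patients per arm (9.2); one-sided Fisher test at 0.10 (9.2). Assumptions, not in the documents: true response 30% in both arms under the null, 50% (A) vs 30% (B) under the alternative; non-evaluable patients are non-responders; evaluable counts are binomial; response among evaluable patients is p/(1 − loss). Rejection probabilities come from exact enumeration.

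**Denominator: chance of rejecting in favour of Arm A when both arms respond at 30%.**

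| Loss A / B | Rejection |
|---|---|
| 0 / 0 (all counted) | 0.062 |
| 10% / 10% | 0.064 |
| 10% / 5% | 0.086 |
| 12.5% / 5% | 0.0997 |
| 13% / 5% | 0.103 |
| 15% / 5% | 0.116 |
| 5% / 15% | 0.031 |

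**A scale for early deaths.** With exponential survival, the fraction dead before the first 8-week scan (1.84 months) is 1 − 2^(−1.84/median). The overall-survival figures in the documents are 10 months (Section 1.1) and 15 to 19 months (Section 1.3). They give 12.0%, 8.2% and 6.5%. These are probably too high: entry requires a life expectancy of at least 12 weeks, and deaths after documented progression stay evaluable. The source populations also included small cell disease (for the Section 1.3 studies, likely), which this trial excludes.

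Next suppose Arm A's early-death hazard is 0.6 times Arm B's, borrowing the design PFS hazard ratio:

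| Median (months) | Loss A / B | Null rejection | Power, 50% vs 30% |
|---|---|---|---|
| 10 | 7.4% / 12.0% | 0.047 | 0.573 |
| 15 | 5.0% / 8.2% | 0.052 | 0.590 |
| 19 | 4.0% / 6.5% | 0.055 | 0.597 |

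With everyone counted, power is 0.624, so the cost is 2.7 to 5.0 points. With the losses reversed, null rejection is 0.085 (12.0% / 7.4%) and about 0.074 (6.5% / 4.0%), still below 0.10.

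**Choice of test, all 39 per arm counted.**

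- Fisher: size 0.045, 0.058, 0.062 and 0.070 at response rates of 10%, 15%, 30% and 50%; power 0.624 for 50% vs 30%.
- Boschloo's exact test: maximum size 0.099 over all response rates; power 0.702.
- CMH over the four randomization strata, 200,000 simulations per setting (assumed: 5-10% PS 2, 30-50% pancreatic, prognostic odds ratios 1 to 3): power about 0.70 to 0.73; size about 0.10, rising to about 0.106-0.107 at a 10% response rate.
- Unstratified Mantel-Haenszel in the same simulations: power 0.708 to 0.717. Stratification itself therefore moves power by only about −1 to +1.4 points. Nearly all of the gain comes from avoiding Fisher's conservatism.

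**The case against.** The best defence is that 9.2 already answers the question. It gives one analysis set, then lists PFS, OS and response without a new set, and states an exception only for toxicity. Section 6.1.1 sits under measurement of effect, says whose response is classified and never mentions an analysis set. A patient with no recorded CR or PR can simply be a non-responder in the 9.2 set. This stands as the natural default. It does not supply the missing sentence on unclassified patients, and the restrictive word in 6.1.1 still lets a second analyst defend another denominator.

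The documents also limit the losses. Measurable disease is an entry criterion (3.1.4). Treatment should start within ten working days of randomization (Section 4). Early objective progressors stay evaluable (6.1.1). Follow-up for response continues after early discontinuation (5.6). For symptomatic deterioration, 6.1.4.4 asks sites to make every effort to document objective progression even after treatment stops. Any re-evaluation qualifies, not only the 8-week scan.

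A reader might infer that the plan commits to an evaluable-only analysis, or that its false-positive rate is inflated. Neither is supported. No passage adopts 6.1.1 as the test's denominator, and inflation above 0.10 needs a gap in losses that no document suggests. The complete-case rule in 9.7.1 shows nothing about the Fisher test: that exploratory analysis cannot run without both values.

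On the test, it is fair to say that Fisher is valid and that the choice is partly preference. The case for changing it is power, not error.

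**Conclusion.** The point holds as a minor one. The response denominator and the handling of unassessed patients should be stated, although all randomized eligible patients is the natural reading. The harm depends on unequal losses, and all loss rates here are assumptions. Equal losses do little. The early-death scenario with a hazard ratio of 0.6 makes the test more conservative (size about 0.05) and costs roughly 3 to 5 points of power. At a 30% response rate, size passes 0.10 only at about 13% loss in Arm A against 5% in Arm B.

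Separately, the Fisher test gives up about 8 to 11 points of power for 50% vs 30%, relative to the alternatives above. That is a loss of efficiency; a reader should not take it as a validity problem. Response is a secondary endpoint and does not drive sample size, the interim efficacy analysis or futility, all of which rest on PFS.

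**What to change.** In 9.2, with a cross-reference in 6.1.1, state that:

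- response rate is CR plus PR over all randomized eligible patients;
- patients without a post-baseline assessment, including those never treated, count as non-responders;
- the rate among patients evaluable under 6.1.1 is reported by arm as supportive only.

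Also in 9.2, replace the Fisher test with a one-sided CMH test at 0.10 stratified by ECOG PS and GI vs pancreatic origin. If guaranteed size matters more than use of the strata, use Boschloo's exact test instead.

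The cost is a few sentences and no new data. Reported response rates will be slightly lower in both arms. The CMH test's size is approximate, up to about 0.107 at a 10% response rate. Boschloo's test keeps its maximum size at 0.099 but does not stratify. The wording should be settled before response is compared by arm.
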